## Statistical Analysis Plan

Sponsor:	Gyroscope Therapeutics		
Protocol:	GT005-01 (FOCUS)		
Document Version No.:	04.0	Document Date:	17-JUN-2024

treatment dose, and route of administration. Plots for mean changes from baseline for BCVA, LLVA and LLD (with 95% CI) over time will be presented.

All BCVA, LLVA and LLD assessments will be provided in data listings.

### 3.9.3. Laboratory Data

Laboratory parameters listed in Table 6 will be presented graphically using boxplots of absolute change from baseline values by treatment dose and route administration and by visit. No summary by visit tables will be provided.

A summary table with counts and percentage of patients satisfying the criteria representing clinically relevant abnormalities defined in Table 6 at any visit will be presented. A listing for patients satisfying at least one criterion in Table 6 at any visit will also be presented.

**Table 6** Clinically notable laboratory values

Test	Critically Low	Critically High	Units
Hemoglobin	< 7.0	> 20.0	g/dL
White Cell Count	< 2.0	> 35.0	$\times 10^3/\mu\text{L}$
Platelets	< 50	> 1000	$\times 10^3/\mu\text{L}$
Glucose	< 40	> 500	mg/dL
Calcium	< 6.0	> 12.0	mg/dL
Phosphate	< 0.9		mg/dL
Sodium	< 120	> 160	mmol/L
Potassium	< 3.0	> 6.0	mmol/L
Magnesium	< 0.74	> 1.0	mmol/L
AST		41	U/L
ALT		45	U/L
Total bilirubin		21	umol/L

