##### 3.1.1. Study days and visit windows

Study day is defined as the number of days relative to the date of the subretinal injection with the study drug. For a particular date, study day will be calculated as follows:

- for dates on or after the date of study treatment: Study day = Assessment date – Date of treatment administration + 1;
- for dates prior to the date of administration of study treatment: Study day = Assessment date – Date of treatment administration.

Baseline values are defined as values from the last assessment prior to surgery for the study treatment administration. All data collected after the treatment administration are defined as post-baseline.

The end of study date is the date when a patient completes or discontinues the study. For reporting data by visit in outputs, the end of study visit will be allocated to the actual (reported) visit number. If the end of study date is not on a scheduled visit, then the end of study visit will be allocated, based on study day, to the closest future scheduled study visit.

For scheduled visits, the analysis visits will be the actual (reported) visits.

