### 3.9.4. Vital Signs

A summary table with counts and percentage of patients satisfying the criteria given in Table 7 at least at one visit will be presented. A listing for patients satisfying at least one criterion in Table 7 will also be presented.

A line plot of mean change from baseline in the vital sign parameters listed in Table 7 by study visit and by treatment dose and route administration with error bars representing 95% CI will be presented. The x-axis will be study visit and the y-axis will be the mean change from baseline value.

[figure not shown]
**Table 7** Clinically notable vital signs

Variable	Category	Critical values
Systolic blood pressure (mmHg)	High	Either >180 with an increase from baseline >30 or >200 absolute
	Low	Either <90 with a decrease from baseline >30 or <75 absolute
Diastolic blood pressure (mmHg)	High	Either >105 with an increase from baseline >20 or >115 absolute
	Low	Either <50 with a decrease from baseline > 20 or <40 absolute

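### The notable-laboratory and vital-sign counts (SAP Tables 6 and 7) are not restricted to post-baseline values and, for laboratory limits and absolute vital-sign limits, ignore baseline status, so alone they cannot separate pre-existing from emergent abnormality

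*SAP*

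**What the plan says.** SAP 3.9.3 plans three laboratory outputs for the Table 6 parameters.

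- **Count table.** Counts and percentages of patients "satisfying the criteria representing clinically relevant abnormalities defined in Table 6 at any visit will be presented".
- **Listing.** "A listing for patients satisfying at least one criterion in Table 6 at any visit will also be presented".
- **Plots.** The parameters are "presented graphically using boxplots of absolute change from baseline values by treatment dose and route administration and by visit".

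It adds: "No summary by visit tables will be provided".

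SAP 3.9.4 uses a similar rule for vital signs. A table of patients "satisfying the criteria given in Table 7 at least at one visit will be presented". Table 7 pairs its moderate limits with a change from baseline, but each row also has an absolute limit with no such condition.

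SAP 3.1.1 supplies the terms that would be needed: "Baseline values are defined as values from the last assessment prior to surgery for the study treatment administration". Data collected after treatment administration are defined there as post-baseline. Neither 3.9.3 nor the counting rule in 3.9.4 uses the post-baseline term.

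Table 6 has columns headed critically low and critically high. Typical rows are "Hemoglobin < 7.0 > 20.0 g/dL" and "Magnesium < 0.74 > 1.0 mmol/L". AST 41 U/L, ALT 45 U/L and total bilirubin 21 umol/L stand in the high column without a comparison sign.

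**The concern.** All participants receive GT005 (Protocol 6.6), and the untreated fellow eye is no comparator for a blood test. A patient's own baseline is therefore the only within-study reference for laboratory safety. The readable eligibility criteria (Protocol 4.2 and 4.3) set no numeric laboratory limit, so a patient may enter already beyond a Table 6 limit and would be counted.

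The SAP draws this distinction elsewhere: 3.9.1 restricts the adverse event tables to treatment-emergent events, and Table 7 asks for a change from baseline at its moderate limits. Table 6 does neither.

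The count carries more weight than usual because the by-visit tables are gone. Protocol 11.3.4.3 promises descriptive statistics and change from baseline over time, while SAP section 4 declares no change from the protocol. A reader who takes the tabulated percentage as on-treatment abnormality would be partly reading the condition of patients at entry.

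**Working it through.** The plan states no expected count for this table, so there is no figure of its own to reproduce. The only related total is enrolment: 3 x 5 + 20 + 2 x 5 + 20 = 65, as stated.

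**Step 1: which draws the rule admits.** Protocol section 7 schedules biochemistry and haematology at Visit 1 (screening) and at Weeks 1, 5, 12, 24, 36 and 48. That is 7 scheduled draws, 1 of them before dosing (1/7 = 14%). If screening is extended, the laboratory tests are repeated, which adds pre-dose draws.

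**Step 2: how much this could move a count.** The documents give no background rate for any Table 6 limit. The flag rate per draw, p, and the within-patient correlation, rho, are therefore assumptions: p from 0.025 to 0.10 and rho from 0 to 0.9, with no drug effect, one limit at a time.

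For independent draws:

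- Flagged at any visit: 1 - (1 - p)^7. At p = 0.025 this is 0.162.
- Flagged post-dose only: 1 - (1 - p)^6 = 0.141.
- Flagged post-dose and not met pre-dose: (1 - p) x [1 - (1 - p)^6] = 0.975 x 0.141 = 0.137.
- Share of flagged patients who already met the limit pre-dose: p / 0.162 = 15%.
- Share flagged solely by the pre-dose draw: 0.025 x 0.975^6 / 0.162 = 13%.

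For correlated draws the same quantities were simulated (400,000 patients, equicorrelated normal values, 7 draws). The rho = 0 rows are also simulated, so they can differ from the formulas in the last digit.

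| p | rho | Any visit | Post-dose only | Post-dose, not met pre-dose | Already met pre-dose (share of flagged) | Pre-dose alone (share of flagged) |
|---|---|---|---|---|---|---|
| 0.025 | 0 | 16.3% | 14.1% | 13.7% | 15% | 13% |
| 0.025 | 0.9 | 5.7% | 5.4% | 3.2% | 44% | 5% |
| 0.05 | 0 | 30.1% | 26.5% | 25.1% | 17% | 12% |
| 0.05 | 0.7 | 15.9% | 14.8% | 10.9% | 32% | 7% |
| 0.05 | 0.9 | 10.4% | 10.0% | 5.4% | 48% | 4% |
| 0.10 | 0 | 52.2% | 47.0% | 42.2% | 19% | 10% |
| 0.10 | 0.9 | 19.0% | 18.3% | 8.9% | 53% | 4% |

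In 65 patients at p = 0.05 and rho = 0.7, the expected counts are 10.3 at any visit, 9.6 post-dose only, and 7.1 post-dose and not met pre-dose. Dropping the screening draw changes little. Removing or identifying patients who met the limit at baseline changes more, especially when values are stable within a patient.

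**Step 3: are the Table 6 limits at one level of severity?** The table itself cannot settle this. The ratio of high to low limit is 1.0/0.74 = 1.35 for magnesium and 160/120 = 1.33 for sodium, so magnesium's band is not unusually narrow by that measure. AST, ALT and bilirubin have a high limit only, and no reference ranges are given. What can be seen is that these three rows lack a sign where every other limit in the table has one. Units are also mixed: calcium and phosphate are in mg/dL, magnesium in mmol/L and bilirubin in umol/L.

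**The case against.** The strongest reply is that the SAP does not rely on the counts alone. The boxplots show change from baseline by dose, route and visit for every Table 6 parameter, the listing identifies flagged patients, and an abnormal laboratory finding can also be reported as an adverse event and tabulated as treatment-emergent. This stands. A reader might infer that the counts will not show treatment-related abnormality, or that a real signal would be hidden. The documents do not support that: post-dose crossings are still counted, and the other displays remain.

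It can also be said that a post-baseline reading was intended, since SAP 3.1.1 describes maximum and minimum summaries as based on post-baseline values. That sentence governs data from unscheduled visits and does not say how Table 6 is built. The intention is plausible, but the counting rule does not state it.

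A reader might further take AST, ALT, bilirubin and magnesium for ordinary reference limits and conclude that most healthy patients would be flagged. That needs laboratory ranges the documents do not give. It also needs independence between repeat draws and between analytes, and pooling of four rows, although meeting at least one criterion is the rule stated for the listing and not for the count table. No such rate is claimed here.

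The missing signs may be only typographical, since the column heading gives the direction. If they are present in the source SAP file, that part falls away. For Table 7 the gap is limited to the absolute limits, because the moderate ones already require a change from baseline.

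**Conclusion.** The point holds in a limited form. Read literally, the Table 6 count, and the Table 7 count at its absolute limits, include pre-dose values and take no account of baseline status. The counts therefore cannot by themselves separate pre-existing from treatment-emergent abnormality. For laboratory data this is the only tabulated output that SAP 3.9.3 plans; the boxplots and the listing partly compensate.

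In the illustration, 15% to 53% of flagged patients already met the limit before dosing, and 4% to 13% were flagged only then. These figures rest on the assumed flag rates and correlations, one limit at a time, 7 draws and no drug effect. They show the order of the effect and do not forecast this trial's counts. Whether the AST, ALT, bilirubin and magnesium limits are at the critical level that the column headings state is an open question for the sponsor.

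**What to change.** In SAP 3.9.3 and 3.9.4, restrict the counts to post-baseline values as defined in 3.1.1. Beside each count, show how many of those patients already met the same criterion at baseline, or instead count patients who met it post-baseline and not at baseline. Keep pre-dose values in the listings, marked as such.

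In Table 6, supply the comparison sign for AST, ALT and total bilirubin. Confirm against the central laboratory's ranges that these rows and magnesium are meant to be at the critical level, and state the basis of each limit.

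The cost is a few lines of SAP text, one programming flag and a check with the laboratory. No new data are needed. Reported counts will fall or be split, and the listings will still show every flagged value.

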### 3.9.4. Vital Signs

A summary table with counts and percentage of patients satisfying the criteria given in Table 7 at least at one visit will be presented. A listing for patients satisfying at least one criterion in Table 7 will also be presented.

A line plot of mean change from baseline in the vital sign parameters listed in Table 7 by study visit and by treatment dose and route administration with error bars representing 95% CI will be presented. The x-axis will be study visit and the y-axis will be the mean change from baseline value.

[figure not shown]
**Table 7** Clinically notable vital signs

Variable	Category	Critical values
Systolic blood pressure (mmHg)	High	Either >180 with an increase from baseline >30 or >200 absolute
	Low	Either <90 with a decrease from baseline >30 or <75 absolute
Diastolic blood pressure (mmHg)	High	Either >105 with an increase from baseline >20 or >115 absolute
	Low	Either <50 with a decrease from baseline > 20 or <40 absolute

## Statistical Analysis Plan

Sponsor:	Gyroscope Therapeutics		
Protocol:	GT005-01 (FOCUS)		
Document Version No.:	04.0	Document Date:	17-JUN-2024

Pulse rate (bpm)	High	Either >120 with an increase from baseline of >25 or > 130 absolute
	Low	Either <50 with a decrease from baseline >30 or <40 absolute

### 3.10. Interim analyses

Interim analyses will present patient disposition, demographic and baseline characteristics and present analysis of selected safety, efficacy and assay variables using methods outlined in the corresponding sections. A reduced number of variables will be reported in the interim analyses.

Ocular baseline characteristics in the study eye will include:

- Study eye selection (left eye OS or right eye OD)
- Best corrected visual acuity BCVA (in ETDRS letters)
- Low-luminance visual acuity LLVA (in ETDRS letters)

## Statistical Analysis Plan

Sponsor:	Gyroscope Therapeutics		
Protocol:	GT005-01 (FOCUS)		
Document Version No.:	04.0	Document Date:	17-JUN-2024

- Low-luminance deficit (BCVA-LLVA, in ETDRS letters)
- GA lesion area (mm^2) as assessed by FAF
- GA contour (Unifocal, Multifocal) as assessed by FAF
- GA foveal involvement (Foveal, Extrafoveal) as assessed by FAF and OCT
- Junctional zone pattern (Atypical, Banded, Diffuse, Focal, Cannot Grade) as assessed by FAF
- [REDACTED]
- Years since GA diagnosis

Analysis of GA area size (mm^2) and square root of GA area size (mm) in the study eye.

Scatter plots with linear trend lines for square root of GA area size (mm) change from baseline at the target analysis visit vs. last observed CFI levels before the target analysis visit in the vitreous and aqueous samples by treatment groups.

Treatment-emergent adverse events summary tables

- Ocular and non-ocular TEAEs by System Organ Class and Preferred Term
- [REDACTED]

BCVA: mean BCVA change from baseline plot in study eye by treatment dose.

The interim reports with Orbit SDS administration cohorts will include the rate of successful full dose delivery of GT005 to the subretinal space and the rate of successful delivery of balanced salt solution (BSS) or BSS PLUS to the subretinal space.

For interim analyses with cutoff visits different between transvitreal and Orbit SDS cohorts, the safety summary tables will be presented for all cohorts up to last common visit (i.e., Week 48 for second interim analysis) and separately for transvitreal administration cohorts up to later cutoff visit (i.e., Week 96 for second interim analyses).

### 3.11. Prior and concomitant therapies

Prior therapies (medications, non-drug therapies and procedures) are defined as therapies completed prior to the study treatment. Concomitant therapies are those received after the start of study treatment including those already started prior to the start of the study treatment.

Prior and concomitant medications will be coded according to the WHO Drug Reference List dictionary,

## Statistical Analysis Plan

Sponsor:	Gyroscope Therapeutics		
Protocol:	GT005-01 (FOCUS)		
Document Version No.:	04.0	Document Date:	17-JUN-2024

---

with maximum coded Anatomical Therapeutic Classification (ATC) level and preferred term.

Prior and concomitant medications, non-drug therapies and procedures will be listed for each treatment dose and administration.

There are no prohibited concomitant medications/procedures for this study, no summary table will be produced.

## Statistical Analysis Plan

Sponsor:	Gyroscope Therapeutics		
Protocol:	GT005-01 (FOCUS)		
Document Version No.:	04.0	Document Date:	17-JUN-2024

### 4. CHANGES TO PLANNED ANALYSES

As of this date, there have been no changes between the protocol-defined statistical analyses and those presented in this statistical plan.

## Statistical Analysis Plan

Sponsor:	Gyroscope Therapeutics		
Protocol:	GT005-01 (FOCUS)		
Document Version No.:	04.0	Document Date:	17-JUN-2024

---

